5.3 Flowchart of the study cohort assembly

	OPTUM		MARKETSCAN	
	Less Excluded	Remaining	Less Excluded	Remaining
	Patients	Patients	Patients	Patients
All patients		79,335,559		200,203,908
Did not meet cohort entry criteria	-77,381,938	1,953,621	-196,683,354	3,520,554
Excluded due to insufficient enrollment	-308,951	1,644,670	-522,438	2,998,116
Excluded due to prior use of referent	-274,142	1,370,528	-362,567	2,635,549
Excluded due to prior use of exposure	-641,980	728,548	-1,225,388	1,410,161
Excluded because patient qualified in >1 exposure category	-10,386	718,162	-17,868	1,392,293

Excluded based on Missing/Unknown Age	-6	718,156	-1	1,392,292
Excluded based on Missing/Unknown Gender	-125	718,031	0	1,392,292
Excluded based on Inclusion #1 - Age 40 to 80 years old	-5	718,026	0	1,392,292
Excluded based on Inclusion #3a - Diagnosis of COPD	-471,394	246,632	-1,038,792	353,500
Excluded based on Inclusion #3b - Clinical history of at least 1 COPD Exacerbation	-110,352	136,280	-153,003	200,497
Excluded based on Exclusion #1 - COPD exacerbation in the 6 weeks prior	-33,666	102,614	-34,019	166,478
Excluded based on Exclusion #2a - Current asthma	-13,344	89,270	-13,539	152,939
Excluded based on Exclusion #2b - Current eczema, atopic dermatitis and/or allergic rhinitis	-5,978	83,292	-7,929	145,010
Excluded based on Exclusion #3 - Has a known respiratory disorder other than COPD	-15,367	67,925	-20,732	124,278
Excluded based on Exclusion #4 - Has narrow-angle glaucoma, prostatic hyperplasia or				
obstruction of the neck of the bladder	-3,927	63,998	-5,648	118,630
Excluded based on Exclusion #5 - Has undergone lung transplantation and/or lung volume				
reduction	-11	63,987	-41	118,589
Excluded based on Exclusion #7 - Requires regular (daily) long-term oxygen therapy (LTOT)	-2,422	61,565	-1,401	117,188
Excluded based on Exclusion #8 - Is receiving beta-blockers (except eye drops)	-7,770	53,795	-14,196	102,992
Excluded based on Exclusion #11 - Has evidence of alcohol, drug or solvent abuse	-945	52,850	-793	102,199
Excluded based on Exclusion #14 - Exclude use of Salmeterol, tiotropium, and fluticasone				
containing inhaler use	-591	52,259	-819	101,380
Final cohort		52,259		101,380

6 Variables

6.1 Exposure-related variables:

Study drug:

The study exposure of interest is initiation of SFC (LABA/ICS combination). Initiation will be defined by no use of inhaled SFC during the prior 180 days before treatment initiation (washout period).

Comparator agents:

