Patient Group	Optum Median Follow- Up Time (Days) [IQR]	Marketscan Median Follow- Up Time (Days) [IQR]
Overall Patient Population	88 [88, 162]	113 [88, 180]
Referent – Tiotropium	88 [88, 160]	99 [88, 175]
Exposure – Salmeterol/Fluticasone	88 [88, 165]	120 [88, 188]

• Report overall risk of the primary outcome.

·	Optum	MarketScan	Pooled
Risk per 1,000 patients	152.99	138.80	143.63

10. Final Power Assessment

Date conducted: 7/15/2021

• Re-calculate power in the appropriate excel table, using the revised number of matched patients from the PS-match in Section 9. All other parameters in the table should be the same as in Section 8.

	ı
Superiority Analysis (Pooled)	
Number of patients matched	
Reference	49,138
Exposed	49,139
Risk per 1,000 patients	143.63
Desired HR from RCT	0.85
Alpha (2-sided)	0.05
Number of events expected	14115.52551
Power	1

Superiority Analysis (Optum)	
Number of patients matched	
Reference	18,017
Exposed	18,017
Risk per 1,000 patients	152.99
Desired HR from RCT	0.85
Alpha (2-sided)	0.05
Number of events expected	5512.84166
Power	0.999976837

Superiority Analysis (Marketscan)		
Number of patients matched		
Reference	31,122	
Exposed	31,122	
Risk per 1,000 patients	138.80	
Desired HR from RCT	0.85	
Alpha (2-sided)	0.05	
Number of events expected	8639.4672	
Power	0.99999989	

• Stop analyses until balance and final power assessment are reviewed by primary investigators, FDA, and assigned members of advisory board.

Reviewed by PI:	[name]	Date reviewed:	
Reviewed by FDA:		Date reviewed:	
Reasons for stopping			
analysis (if required):			

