Appendix A: COPD Exacerbation (primary outcome), All-cause mortality (secondary outcome)

COPD Exacerbation

Measured 1 day after drug initiation in primary diagnosis position specified below and inpatient care setting -

COPD (Inpatient, Primary)

ICD-9 Diagnosis: 491.x, 492.x, 496 ICD-10 Diagnosis: J41.x, J42, J43.x, J44.x

OR

Measured 1 day after drug initiation in any diagnosis position specified below and inpatient and outpatient care setting AND steroid use within 14 days -

COPD (Any care setting, Any position)

ICD-9 Diagnosis: 491.x, 492.x, 496 ICD-10 Diagnosis: J41.x, J42, J43.x, J44.x

AND

Corticosteroid systemic administration and/or oral prescription of --

- Prednisone
- Prednisolone
- Methylprednisolone
- Dexamethasone
- Hydrocortisone

All-Cause Mortality

Identified using the discharge status codes-

Optum-Inpatient/Outpatient

- 20 = EXPIRED
- 21 = EXPIRED TO BE DEFINED AT STATE LEVEL
- 22 = EXPIRED TO BE DEFINED AT STATE LEVEL
- 23 = EXPIRED TO BE DEFINED AT STATE LEVEL
- 24 = EXPIRED TO BE DEFINED AT STATE LEVEL

- 25 = EXPIRED TO BE DEFINED AT STATE LEVEL
- 26 = EXPIRED TO BE DEFINED AT STATE LEVEL
- 27 = EXPIRED TO BE DEFINED AT STATE LEVEL
- 28 = EXPIRED TO BE DEFINED AT STATE LEVEL
- 29 = EXPIRED TO BE DEFINED AT STATE LEVEL
- 40 = EXPIRED AT HOME (HOSPICE)
- 41 = EXPIRED IN A MEDICAL FACILITY (HOSPICE)
- 42 = EXPIRED PLACE UNKNOWN (HOSPICE)

Marketscan-Inpatient

- 20 Died
- 22 Died
- 23 Died
- 24 Died
- 25 Died
- 26 Died
- 27 Died
- 28 Died
- 29 Died
- 40 Other died status or Expired at home (Hospice claims only) (depends on year)
- 41 Other died status or Expired in medical facility (Hospice claims only) (depends on year)
- 42 Other died status or Expired place unknown (Hospice claims only) (depends on year)
- 21 Died or Disch./Transf. to court/law enforcement (depends on year)

#	INSPIRE trial definitions	Implementation in routine care	References/Rationale	Color coding
			Please see the following Google drive for further details or any missing information_ https://drive.google.com/drive/fold ers/1WD618wrywYjEaXzfLTcuK-	
	Trial details - Intended S with label change - 2 weeks run-in		VCcnb6b-gV	Criteria
	EXPOSURE vs. COMPARISON			Adequate mapping in claims
	Tiotropium 18 mcg once daily vs. Salmeterol/fluticasone propionate (SFC) 50/500 mcg twice daily	SFC vs. Tiotropium		Intermediate mapping in

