1	COPD exacerbation in the 6 weeks prior to screening	Measured 42 days prior to and including the day of drug initiation in prescription claims COPD (Inpatient, Any) ICD-9 Diagnosis: 491.x, 492.x, 496.0 ICD-10 Diagnosis: J41.x, J42, J43.x, J44.x OR COPD (Any care setting, Any position) ICD-9 Diagnosis: 491.x, 492.x, 496.0 ICD-10 Diagnosis: J41.x, J42, J43.x, J44.x AND Corticosteriod systemic administration and/or prescription - Prednisone - Prednisolone - Methylprednisolone - Dexamethasone - Hydrocortisone

[figure not shown]
		7
		Measured 180 days prior to and including the day of drug initiation in any diagnosis position in the inpatient and outpatient care setting
		A 11 /0 P: 111: 400 L 3
		Asthma (3 Diagnosis within 180 days)
		ICD-9 Diagnosis: 493.x
		ICD-10 Diagnosis: J45.x
		Eczema
		ICD-9 Diagnosis: 692.x
2	Current asthma, eczema, atopic dermatitis and/or allergic rhinitis	ICD-10 Diagnosis: L23.x, L24.x
	Current astrima, eczema, atopic dermatitis and/or anergic minitis	
		Atopic dermatitis
		ICD-9 Diagnosis: 691.x
		ICD-10 Diagnosis: L20.x
		To Diagnosis. E20.X
		Allowed
		Allergic rhinitis
I		ICD-9 Diagnosis: 477.x
		ICD10 Diagnosis: J30.x
—		Measured since all available data to and including the day of drug initiation in any diagnosis
		position in the inpatient and outpatient care setting
		position in the imputions and outputions care setting
I		Dulmanary Fibracia ay Interstitial Lung Disease (U.S.)
I		Pulmonary Fibrosis or Interstitial Lung Disease (ILD)
		ICD-9 Diagnosis: 515, 516.3x, 516.8, 516.9
I		ICD-10 Diagnosis: J84.10, J84.111, J84.112, J84.113, J84.114, J84.115, J84.116, J84.117, J84.09,
		J84.2, J84.89, J84.9
		L
		Sarcoidosis
		ICD-9 diagnosis: 135
		ICD-10 diagnosis: D86.0, D86.2
3	Has a known respiratory disorder other than COPD (e.g. lung cancer, sarcoidosis, tuberculosis or lung fibrosis)	Lymphangioleiomyomatosis
ľ	Thas a known respiratory disorder other than corp (e.g. rung cancer, sarcoldosis, tuberculosis or rung runosis)	ICD-9 diagnosis: 516.4
		ICD-10 diagnosis: J84.81
		Primary/Pulmonary Tuberculosis
		ICD-9 diagnosis: 010.x, 011.x
		ICD-10 diagnosis: A15.x
		Cystic Fibrosis
I		ICD-9 Diagnosis: 277.0x
		ICD-10 Diagnosis: E84.xx
I		Pulmonary Hypertension/Other Pulmonary Heart Disease
		ICD-9 Diagnosis: 416 vy
		Measured 180 days prior to and including the day of drug initiation in any diagnosis position in the inpatient and outpatient care setting
		Narrow-angle Glaucoma
I		

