PRX - LAMA (except tiotropium) inhalers; n (%)	79 (0.4%)	129 (0.7%)	-0.0406	104 (0.3%)	160 (0.5%)	-0.0317	183 (0.4%)	289 (0.6%)	-0.028
PRX - ICS only inhalers; n (%)	2,225 (12.3%)	2,173 (12.1%)	0.0061	5,212 (16.7%)	5,163 (16.6%)	0.0027	7,437 (15.1%)	7,336 (14.9%)	0.006
PRX - LABA/LAMA inhaler use ; n (%)	114 (0.6%)	80 (0.4%)	0.0284	56 (0.2%)	42 (0.1%)	0.0258	170 (0.3%)	122 (0.2%)	0.020
PRX - Other LABA/ICS combination ; n (%)	916 (5.1%)	892 (5.0%)	0.0046	1,495 (4.8%)	1,469 (4.7%)	0.0047	2,411 (4.9%)	2,361 (4.8%)	0.005
PRX - COPD Maintenance therapy inhalers; n (%)	1,183 (6.6%)	1,169 (6.5%)	0.0040	1,729 (5.6%)	1,698 (5.5%)	0.0044	2,912 (5.9%)	2,867 (5.8%)	0.004
PRX - SAMA inhaler use; n (%)	656 (3.6%)	654 (3.6%)	0.0000	1,405 (4.5%)	1,431 (4.6%)	-0.0048	2,061 (4.2%)	2,085 (4.2%)	0.000
PRX - SABA use; n (%)	8,121 (45.1%)	8,083 (44.9%)	0.0040	13,827 (44.4%)	13,671 (43.9%)	0.0101	21,948 (44.7%)	21,754 (44.3%)	0.008
PRX - SABA/SAMA use; n (%)	2,035 (11.3%)	2,140 (11.9%)	-0.0187	4,133 (13.3%)	4,220 (13.6%)	-0.0088	6,168 (12.6%)	6,360 (12.9%)	-0.009
PRX - Antibiotics treatment (180 days to 31 days before CED); n (%)	6,629 (36.8%)	6,636 (36.8%)	0.0000	12,467 (40.1%)	12,337 (39.6%)	0.0102	19,096 (38.9%)	18,973 (38.6%)	0.006
PRX - Antibiotics treatment (30 days to CED); n (%)	2,690 (14.9%)	2,627 (14.6%)	0.0085	5,514 (17.7%)	5,441 (17.5%)	0.0053	8,204 (16.7%)	8,068 (16.4%)	0.008
PRX - Systemic Corticosteroids (with CPT) use (180 to 31 days before CED); n (%)	5,612 (31.1%)	5,577 (31.0%)	0.0022	9,580 (30.8%)	9,597 (30.8%)	0.0000	15,192 (30.9%)	15,174 (30.9%)	0.000

PRX - Systemic Corticosteroids (with CPT) use (30 days to CED); n (%)	1,016 (5.6%)	940 (5.2%)	0.0177	2,352 (7.6%)	2,284 (7.3%)	0.0114	3,368 (6.9%)	3,224 (6.6%)	0.012
PRX - Roflumilast; n (%) *	40 (0.2%)	31 (0.2%)	0.0000	102 (0.3%)	53 (0.2%)	0.0200	142 (0.3%)	084 (0.2%)	0.020
CVD the stable and the (Ather 197)	400 (2 00)	464 (2.69()	0.0000	FOC (4.00()	500 (4.00/)	0.0000	1,064 (2.2%)	1,062 (2.2%)	0.000
CVD - Unstable angina/MI; n (%) CVD - Stable Angina : n (%)	468 (2.6%) 318 (1.8%)	464 (2.6%) 314 (1.7%)	0.0000	596 (1.9%) 482 (1.5%)	598 (1.9%) 476 (1.5%)	0.0000	800 (1.6%)	790 (1.6%)	0.000
CVD - Any Heart failure (HF); n (%)	1,108 (6.1%)	1,131 (6.3%)	-0.0083	1,797 (5.8%)	1,807 (5.8%)	0.0000	2,905 (5.9%)	2,938 (6.0%)	-0.004
CVD - Atrial fibrillation; n (%)	911 (5.1%)	911 (5.1%)	0.0000	1,480 (4.8%)	1,488 (4.8%)	0.0000	2,391 (4.9%)	2,399 (4.9%)	0.000

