ORX - Use of antiplatelet agents ; n (%)*	1,174 (6.5%)	1,104 (6.1%)	0.0165	3,085 (9.9%)	2,922 (9.4%)	0.0169	4,259 (8.7%)	4,026 (8.2%)	0.018
				, ,					
LFS - Obesity; n (%)	1,298 (7.2%)	1,310 (7.3%)	-0.0039	1,289 (4.1%)	1,290 (4.1%)	0.0000	2,587 (5.3%)	2,600 (5.3%)	0.000
PFT - Spirometry test only; n (%)	3,180 (17.6%)	3,028 (16.8%)	0.0212	7,080 (22.7%)	6,932 (22.3%)	0.0096	10,260 (20.9%)	9,960 (20.3%)	0.015
PFT - Spirometry test only (Count - 180 days to 31 days before CED) *mean (sd)	0.18 (0.66)	0.18 (0.65)	0.0000	0.20 (0.64)	0.22 (0.65)	-0.0310	0.19 (0.65)	0.21 (0.65)	-0.031
median [IQR]	0.00 [0.00, 0.00]	0.00 [0.00, 0.00]	0.0000	0.00 [0.00, 0.00]	0.00 [0.00, 0.00]	0.0000	0.00 (0.65)	0.00 (0.65)	0.000
PFT - Spirometry test only (Count - 30 days to CED) *									

mean (sd)	0.14 (0.56)	0.11 (0.48)	0.0575	0.17 (0.55)	0.13 (0.47)	0.0782	0.16 (0.55)	0.12 (0.47)	0.078
median [IQR]	0.00 [0.00, 0.00]	0.00 [0.00, 0.00]	0.0000	0.00 [0.00, 0.00]	0.00 [0.00, 0.00]	0.0000	0.00 (0.55)	0.00 (0.47)	0.000
PFT - Lung volume, Diffuse capacity, pulmonary stress testing (any); n (%)	1,987 (11.0%)	1,910 (10.6%)	0.0129	3,084 (9.9%)	2,970 (9.5%)	0.0135	5,071 (10.3%)	4,880 (9.9%)	0.013
g in g	, , , , , , , , , , , , , , , , , , , ,	, , , , , , , , , , , , , , , , , , , ,		γ ,	, , , , ,				
HCU - Pulmonologist visit (180 to 1 day before CED); n (%)	189 (1.0%)	182 (1.0%)	0.0000	5,646 (18.1%)	5,482 (17.6%)	0.0131	5,835 (11.9%)	5,664 (11.5%)	0.012
HCU - Pulmonologist visit on CED; n (%)	24 (0.1%)	24 (0.1%)	0.0000	949 (3.0%)	932 (3.0%)	0.0000	973 (2.0%)	956 (1.9%)	0.007
HCU - Pulmonologist visit (Number of during CAP) *	' '	` '		· ·	` '				
mean (sd)	0.06 (0.94)	0.07 (0.94)	-0.0106	0.75 (2.21)	0.70 (2.11)	0.0231	0.50 (1.85)	0.47 (1.77)	0.017
median [IQR]	0.00 [0.00, 0.00]	0.00 [0.00, 0.00]	0.0000	0.00 [0.00, 0.00]	0.00 [0.00, 0.00]	0.0000	0.00 (1.85)	0.00 (1.77)	0.000
HCU - Number of Internal Medicine/Family Medicine Visits									
mean (sd)	7.48 (11.28)	7.62 (11.09)	-0.0125	6.14 (9.32)	6.16 (9.74)	-0.0021	6.63 (10.08)	6.70 (10.26)	-0.007
median [IQR]	4.00 [1.00, 10.00]	4.00 [1.00, 10.00]	0.0000	4.00 [1.00, 8.00]	3.00 [1.00, 8.00]	0.1049	4.00 (10.08)	3.37 (10.26)	0.062
HCU - Number of Cardiologist visits									
mean (sd)	0.86 (3.19)	0.86 (2.82)	0.0000	0.79 (2.82)	0.79 (3.36)	0.0000	0.82 (2.96)	0.82 (3.17)	0.000
median [IQR]	0.00 [0.00, 0.00]	0.00 [0.00, 0.00]	0.0000	0.00 [0.00, 0.00]	0.00 [0.00, 0.00]	0.0000	0.00 (2.96)	0.00 (3.17)	0.000

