HCU - Number of Emergency Department (ED) visits v3									
mean (sd)	0.46 (1.29)	0.47 (1.25)	-0.0079	0.17 (1.12)	0.16 (0.95)	0.0096	0.28 (1.19)	0.27 (1.07)	0.009
median [IQR]	0.00 [0.00, 0.00]	0.00 [0.00, 0.00]	0.0000	0.00 [0.00, 0.00]	0.00 [0.00, 0.00]	0.0000	0.00 (1.19)	0.00 (1.07)	0.000
HCU - Old hospitalization (-180 days to -31 days before CED); n (%)	1,508 (8.4%)	1,514 (8.4%)	0.0000	4,137 (13.3%)	4,095 (13.2%)	0.0029	5,645 (11.5%)	5,609 (11.4%)	0.003
HCU - Recent hospitalization (-30 days to CED date); n (%)	166 (0.9%)	166 (0.9%)	0.0000	532 (1.7%)	523 (1.7%)	0.0000	698 (1.4%)	689 (1.4%)	0.000
HCU - Number of hospitalizations during CAP									
mean (sd)	0.11 (0.37)	0.11 (0.37)	0.0000	0.17 (0.43)	0.16 (0.43)	0.0233	0.15 (0.41)	0.14 (0.41)	0.024
median [IQR]	0.00 [0.00, 0.00]	0.00 [0.00, 0.00]	0.0000	0.00 [0.00, 0.00]	0.00 [0.00, 0.00]	0.0000	0.00 (0.41)	0.00 (0.41)	0.000
HCU - Blood eosinophilia or Serum IgE test order; n (%)*	85 (0.5%)	93 (0.5%)	0.0000	113 (0.4%)	136 (0.4%)	0.0000	198 (0.4%)	229 (0.5%)	-0.015
HCU - Pneumococcal vaccine; n (%)	2,119 (11.8%)	2,112 (11.7%)	0.0031	1,615 (5.2%)	1,601 (5.1%)	0.0045	3,734 (7.6%)	3,713 (7.6%)	0.000
HCU - Flu vaccine ; n (%)	3,385 (18.8%)	3,370 (18.7%)	0.0026	3,684 (11.8%)	3,659 (11.8%)	0.0000	7,069 (14.4%)	7,029 (14.3%)	0.003
HCU - Bone mineral density ; n (%)	795 (4.4%)	788 (4.4%)	0.0000	931 (3.0%)	953 (3.1%)	-0.0058	1,726 (3.5%)	1,741 (3.5%)	0.000
HCU - Pap smear; n (%)	711 (3.9%)	707 (3.9%)	0.0000	1,429 (4.6%)	1,419 (4.6%)	0.0000	2,140 (4.4%)	2,126 (4.3%)	0.005
HCU - Mammogram ; n (%)	2,274 (12.6%)	2,273 (12.6%)	0.0000	3,319 (10.7%)	3,340 (10.7%)	0.0000	5,593 (11.4%)	5,613 (11.4%)	0.000
HCU - Prostate exam for DRE; n (%)	542 (3.0%)	545 (3.0%)	0.0000	517 (1.7%)	509 (1.6%)	0.0079	1,059 (2.2%)	1,054 (2.1%)	0.007
HCU - Number of Echocardiogram *									
mean (sd)	0.20 (1.27)	0.19 (1.21)	0.0081	0.23 (0.80)	0.23 (0.84)	0.0000	0.22 (1.00)	0.22 (0.99)	0.000
median [IQR]	0.00 [0.00, 0.00]	0.00 [0.00, 0.00]	0.0000	0.00 [0.00, 0.00]	0.00 [0.00, 0.00]	0.0000	0.00 (1.00)	0.00 (0.99)	0.000
HCU - Flexible Sigmoidoscopy or colonoscopy or CT virtual colonoscopy ; n (%)	816 (4.5%)	808 (4.5%)	0.0000	1,609 (5.2%)	1,634 (5.3%)	-0.0045	2,425 (4.9%)	2,442 (5.0%)	-0.005
HCU - Number of Distinct Medication Prescriptions (not generalized to generics)									
mean (sd)	20.27 (17.04)	20.34 (16.67)	-0.0042	19.34 (15.01)	19.39 (15.01)	-0.0033	19.68 (15.78)	19.74 (15.64)	-0.004

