median [IQR]	16.00 [8.00, 27.00]	16.00 [9.00, 27.00]	0.0000	16.00 [9.00, 26.00]	16.00 [9.00, 26.00]	0.0000	16.00 (15.78)	16.00 (15.64)	0.000
SES - Copay for pharmacy cost (charges in U.S. \$)									
mean (sd)	32.00 (38.05)	31.87 (35.15)	0.0035	25.66 (26.01)	25.75 (26.16)	-0.0035	27.98 (30.97)	27.99 (29.77)	0.000
median [IQR]	23.60 [10.60, 40.25]	24.23 [10.04, 41.52]	-0.0172	20.26 [10.00, 34.37]	20.61 [9.80, 34.59]	-0.0134	21.48 (30.97)	21.94 (29.77)	-0.015
SES - Business type									
Commercial; n (%)	5,963 (33.1%)	5,735 (31.8%)	0.0278				5,963 (33.1%)	5,735 (31.8%)	0.028
Medicare; n (%)	12,054 (66.9%)	12,282 (68.2%)	-0.0278			\perp	12,054 (66.9%)	12,282 (68.2%)	-0.028
SES - Low income indicator ; n (%)	3,483 (19.3%)	3,604 (20.0%)	-0.0176			\perp	3,483 (19.3%)	3,604 (20.0%)	-0.018
SES - Insurance Plan type									
Comprehensive; n (%)				9,074 (29.2%)	9,146 (29.4%)	-0.0044	9,074 (29.2%)	9,146 (29.4%)	-0.004
HMO; n (%)				3,810 (12.2%)	3,763 (12.1%)	0.0031	3,810 (12.2%)	3,763 (12.1%)	0.003
PPO; n (%)				14,372 (46.2%)	14,423 (46.3%)	-0.0020	14,372 (46.2%)	14,423 (46.3%)	-0.002
Others; n (%)				3,866 (12.4%)	3,790 (12.2%)	0.0061	3,866 (12.4%)	3,790 (12.2%)	0.006

^{*} Not included in PS model

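### Patients with one or two asthma codes at baseline can stay in the cohort, and asthma is in neither the propensity score nor the balance tables, so its balance between arms cannot be checked

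*Combined protocol and SAP*

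**What the plan says.** Exclusion 2 in Appendix A covers four conditions: asthma, eczema, atopic dermatitis and allergic rhinitis. All are looked for in the 180 days up to and including initiation, in any diagnosis position. Asthma (493.x, J45.x) alone carries a count: "Asthma (3 Diagnosis within 180 days". The text does not say whether this means at least three, or on separate dates.

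The Section 5.3 flowchart line "Excluded based on Exclusion #2a - Current asthma" removes 13,344 Optum and 13,539 MarketScan patients. The next line removes 5,978 and 7,929 for the atopic conditions. Neither line is split by arm or by number of codes.

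Section 6.2 sends the reader to Table 1 (Appendix B) for the remaining covariates, and Section 9 says that the PS uses the complete list. Starred rows are the exception; the footnote marks them "Not included in PS model". Asthma has no row, starred or unstarred, in the unmatched or the matched table. The nearest row is "HCU - Blood eosinophilia or Serum IgE test order; n", which is starred.

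One route to the primary outcome (Appendix A) is a COPD code in any position, "inpatient and outpatient care setting AND steroid use within 14 days".

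**The concern.** Asthma is a plausible reason to choose an inhaler containing a corticosteroid over tiotropium. It may also lead to systemic steroid courses, and in a patient who carries a COPD code as well, such a course can count as an outcome event. A baseline factor that may be linked to both treatment and outcome would normally be adjusted for, or at least shown to be balanced. Here the heaviest asthma coding is excluded by design, but lighter coding is neither adjusted for directly nor reported.

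The expected event count is large, so random error is small and a systematic error of a few per cent would be of similar size. That matters for a study whose purpose is agreement with a trial rate ratio of 0.967 (Section 1.5).

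**Working it through.** **1. The plan's own precision figures.** Section 10 gives 49,138 + 49,139 matched patients and a risk of 143.63 per 1,000. Expected events = 98,277 × 0.14363 = 14,115.5, as stated. Power at hazard ratio 0.85 is Φ(|ln 0.85| × √events / 2 − 1.96):
- pooled: 1.0000 (stated 1);
- Optum, 5,512.84 events: 0.99998 (stated 0.999976837);
- MarketScan, 8,639.47 events: 0.99999999 (stated 0.99999989, a difference without consequence).

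The approximate pooled 95% half-width on the log scale is 1.96 × 2/√14,115.5 = 0.033, or about 3.3%.

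**2. What the asthma rule removed (Section 5.3).** Optum 13,344/102,614 = 13.0%; MarketScan 13,539/166,478 = 8.1%; together 26,883/269,092 = 10.0%. The number left with one or two codes is not given.

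**3. Related rows in Table 1 (pooled, tiotropium/SFC; SMD = standardised difference).**

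| Row | Before matching | After matching | In PS? |
|---|---|---|---|
| ICS-only inhaler | 15.5/15.9%, SMD -0.011 | 15.1/14.9%, 0.006 | yes |
| SABA | 46.4/45.3%, 0.022 | 44.7/44.3%, 0.008 | yes |
| Eosinophil or IgE test | 0.4/0.5%, -0.015 | 0.4/0.5%, -0.015 | no |
| Mean age (years) | 66.45/63.16, 0.263 | 66.30/66.68, -0.032 | yes |
| Smoking | 22.8/13.3%, 0.249 | 20.2/19.6%, 0.015 | yes |
| Systemic steroids, 30 days | 6.3/11.9% | 6.9/6.6%, 0.012 | yes |

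The three rows closest to asthma were nearly equal before matching. The three that differed are in the PS and are balanced afterwards.

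**4. A benchmark for a covariate left out of the PS.** Among starred means and proportions, the largest pooled post-match difference is 0.078, for "PFT - Spirometry test only (Count - 30 days to CED". Check: (0.16 − 0.12)/√((0.55² + 0.47²)/2) = 0.078. Before matching it was 0.194. Table 1 takes tiotropium minus SFC. Its sign says nothing about asthma, so both directions are worked below.

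**5. Illustrative bias.** Let p0 and p1 be the asthma prevalence in the tiotropium and SFC arms and h the hazard ratio for asthma. All three are assumed, because the documents give none of them. Find p1 from |p1 − p0|/√((p1(1−p1) + p0(1−p0))/2) = 0.078. The bias factor is (1 + p1(h−1))/(1 + p0(h−1)).

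| p0 | p1, SFC higher | Bias, h = 1.2 to 1.5 | p1, SFC lower | Bias, h = 1.2 to 1.5 |
|---|---|---|---|---|
| 5% | 6.8% | +0.4% to +0.9% | 3.4% | -0.3% to -0.8% |
| 10% | 12.5% | +0.5% to +1.2% | 7.8% | -0.4% to -1.1% |
| 20% | 23.2% | +0.6% to +1.5% | 17.0% | -0.6% to -1.4% |

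**6. Less favourable assumptions.** At h = 2 and p0 = 20%, an SMD of 0.078 gives +2.7%. Prevalences of 10% against 20% (SMD 0.28) give 1.020, 1.048 and 1.091 at h = 1.2, 1.5 and 2.

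**7. Break-even.** With p0 = 10%, the bias equals the 3.3% half-width at:
- p1 = 27.1% (SMD 0.45) for h = 1.2;
- p1 = 17.0% (SMD 0.21) for h = 1.5;
- p1 = 13.7% (SMD 0.11) for h = 2.

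**The case against.** The strongest reply is that asthma was handled by design. A tenth of the patients reaching that step were removed for it, the atopic conditions were removed next, and no section requires asthma as a covariate. The closest proxies were almost equal before matching, which gives no support to channelling. The post-match c-statistics are 0.523 and 0.516. The magnitude rests on assumed inputs, and the benchmark is a difference in rounded spirometry counts with no shown link to an asthma flag. Re-matching and renewed review look heavy for a hypothetical bias of about 1%.

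Most of this stands. It makes a large bias less likely, and it is why the calculation is only an illustration. It does not show balance on asthma: proxies and other starred rows cannot do that, and the table already reports many covariates outside the PS.

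Two stronger readings are tempting. A reader might infer that asthma was channelled to SFC and biases the ratio against it, since SFC initiators were younger, had less coded smoking and had more recent steroid use before matching. Those rows are not specific to asthma, are in the PS, and are balanced after matching. A reader might also infer that the three-code threshold is wrong. Appendix A refers to an external folder for further detail, and the colour grading of the mapping is not legible in the text, so a rationale may exist that is not visible here.

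**Conclusion.** The point holds as a gap in adjustment and reporting, not as a demonstrated bias. Patients with one or two asthma codes can remain, asthma is not directly in the PS, and its balance is unreported. Size and direction are unknown.

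The figure of up to about 1.5% either way rests on three assumptions: an imbalance no worse than the worst pooled starred row, a prevalence of 5-20%, and a hazard ratio of 1.2-1.5. It lies below the pooled half-width of about 3.3%. A stronger asthma effect or a larger imbalance could bring the bias level with random error or beyond it, and the documents cannot exclude that. Power at hazard ratio 0.85 is not in question. The change is worth making because it is cheap and settles the matter, with medium confidence that it will alter anything.

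**What to change.** Before any outcome analysis by treatment:

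1. Report any asthma diagnosis (493.x, J45.x) in the 180-day baseline by arm in Table 1, before and after matching. State also whether the exclusion means at least three codes and whether they must fall on separate dates.
2. Add that flag to the PS model.
3. Run one sensitivity analysis excluding patients with at least one asthma diagnosis in the window.

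The codes are already listed. The real cost is re-matching, repeating Sections 9 and 10, and renewed sign-off, since Section 10 says: "Stop analyses until balance and final power assessment are reviewed by primary investigators, FDA, and assigned members of advisory board". Balance was assessed on a dummy outcome, and the documents report no treatment effect, so the change can still be made blind to results.

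The sensitivity analysis loses patients. If it loses 10-25% of the matched cohort (assumption), the events left are 14,115.5 × 0.90 = 12,704 to 14,115.5 × 0.75 = 10,587. The half-width becomes 3.92/√12,704 = 3.5% to 3.92/√10,587 = 3.8%, and power at hazard ratio 0.85 stays above 0.999.

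If re-matching is not acceptable, items 1 and 3 alone are the minimum.
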